## Project Protocol

### **Objective:**

This proposal addresses a highly significant topic, tobacco and opioid addiction among pregnant women, at a time in which opioid addiction is considered a rising national epidemic. Each year, 225,000 infants in the United States are exposed prenatally to illicit drugs. Women with substance use disorders, particularly those with opioid dependence (per DSM-4), are highly vulnerable to cigarette smoking during the perinatal period. Pregnant opioid dependent patients seeking medication-assisted treatment (MAT) have high rates of smoking, ranging from 88% to 95%. Smoking during pregnancy is an independent risk factor (outside of illicit drug use) for several adverse outcomes including ectopic pregnancy, premature birth, orofacial clefts, and sudden infant death syndrome. Illicit opioid use magnifies these risks; among women who use opioids during pregnancy, there is a 6-fold greater risk for intrauterine growth restriction, third trimester vaginal bleeding, preterm delivery, and a majority also will experience neonatal abstinence syndrome (NAS). Prenatal tobacco use significantly increases the severity and duration of NAS, yet is not commonly treated among opioid dependent pregnant women receiving MAT. On average, the healthcare cost per discharged infant with NAS ranges from \$39,400 to \$53,400; and 77.6% is paid for by Medicaid. MAT has been shown to decrease the severity of NAS compared to no treatment; yet, most opioid dependent women in MAT still continue to smoke cigarettes throughout pregnancy, clearly suggesting that there is a significant need for a comprehensive, evidence-based tobacco treatment intervention. To date, there is no specific pharmacologic or non-pharmacologic tobacco-treatment standard for opioid dependent pregnant women in MAT. More research is needed to develop and test tailored tobacco treatment interventions for pregnant, opioid dependent women.

The purpose of this pilot services effectiveness research trial is to test feasibility and efficacy of a Behavioral and Enhanced Perinatal Intervention for Cessation (B-EPIC) of tobacco use in an established MAT clinic. B-EPIC includes four core components: 1) Individualized tobacco treatment plus supplemental counseling, 2) Biomarker validation and feedback, 3) Focus and adoption of healthy behavior, and 4) Pharmacotherapy as needed. The B-EPIC is designed to reduce tobacco-associated morbidity (e.g., preterm birth, NAS) and healthcare expenditures in pregnant women who are tobacco users receiving buprenorphine for opioid dependence. This two-group randomized and controlled clinical trial (n =100) will provide critical preliminary data to test larger-scale trials. As most B-EPIC services are billable services via public and private insurers; there is high likelihood for sustainability.

### **Background Information:**

In the United States (US), opioid use has tripled since the 1990s, with the Centers for Disease Control and Prevention (CDC) now referring to opioid addiction as a national epidemic. Although a higher percentage of men abuse drugs compared to women, the gender gap has lessened. Women who use illicit opioids are a particularly vulnerable population. Women with substance use disorders often have mood (29.7%) and anxiety disorders (26.2%). Rates of sexual or physical abuse among women in substance use disorder treatment facilities range from 55-99%, and 34.4% of individuals with post-traumatic stress disorder also had a substance use disorder. In addition, illicit opioid use among women is highest among women of childbearing age.

Each year, 225,000 infants in the US are exposed prenatally to illicit drugs. Women who abuse opioids during pregnancy have a 6-fold greater risk for intrauterine growth restriction, third trimester vaginal bleeding, preterm delivery, and stillbirth. The use of intravenous opioids raises the risk of infectious diseases (e.g., HIV, hepatitis C

and endocarditis), further complicating pregnancy. Each year, 50,000 infants are treated for neonatal abstinence syndrome (NAS). On average, the healthcare cost per NAS discharge ranges from \$39,400 to \$53,400, and 77.6% of these costs are paid for by Medicaid.

Medication-assisted-treatment (MAT) with methadone remains the standard of care; however, given difficulties with accessing licensed methadone opioid treatment programs (e.g., some states have only one), many rural (and non-rural) women do not access methadone treatment. Buprenorphine can be prescribed in outpatient physician office, which increases access to and decreases the stigma of care. It also has similar efficacy and improved NAS outcomes compared to methadone; thus, it is increasingly accepted and utilized for the outpatient treatment of opioid dependence in pregnancy.

Pregnant women engaged in MAT have high rates of smoking, ranging from 88-95%. Smoking during pregnancy increases the risk of multiple adverse outcomes including ectopic pregnancy, premature birth, orofacial clefts, and sudden infant death syndrome, and the risk continues beyond pregnancy. Children exposed to secondhand smoke (SHS) have an increased risk for asthma and other respiratory disorders, as well as attention deficit hyperactivity disorder and poor neurocognitive performance. Children born to mothers who smoke during pregnancy have a higher risk of nicotine dependence in adulthood than their peers. Further, there is growing evidence that treating tobacco use concurrently with substance use disorder treatment may lead to a greater likelihood of abstinence from alcohol or other drugs.

Smoking during pregnancy also has adverse economic consequences for families and the health care system. Maternal smoking increases the risk of admission to a NICU by as much as 20% in some studies, while also increasing overall hospital length of stay for the newborn infant, resulting in significant smoking-attributable hospital costs during the episode of delivery. Over the longer term, infants born to mothers who smoked during pregnancy are more likely to be readmitted to the hospital during their first year of life, more likely to experience asthma requiring medication use, and are more likely to have emergency room utilization.

The American College of Obstetrics and Gynecologists recommends the 5A's approach for smoking cessation during pregnancy. The integration of a 5A's based tobacco treatment intervention into an MAT clinic for pregnant and parenting women led to a significant reduction in cigarettes per day (49% among pregnant and 32% among non-pregnant clients). However, a very small percentage of the participants stopped smoking, indicating the need for a more intense, tailored intervention for this population. To date, there is no specific treatment standard for pregnant women addicted to opioids. Few tobacco treatment interventions have been tested for pregnant women in MAT One study showed promise utilizing a 12 vs. 6 week intervention that included contingency-behavioral incentives; however long-term abstinence was not measured. Further, effects of contingency incentives often cease after the intervention period ends. There is a need to shift clinical practice for pregnant women who are opioid dependent to include focused intervention on tobacco. We are integrating a pilot proof of concept novel tobacco intervention into an existing MAT program. The majority of addiction in pregnancy treatment programs are located within urban settings despite rural and non-urban residents being disproportionately affected by tobacco and opioid dependence. We will be the first to provide a tobacco treatment intervention among opioid dependent pregnant women in an MAT clinic serving a large proportion of non-urban women. This significantly increases the generalizability and prospect that the B-EPIC intervention could be replicated in both urban and rural communities.

Based on the breadth and depth of evidence summarized above, the premise of the application is to provide a tobacco treatment standard for pregnant women addicted to opioids. Few tobacco treatment interventions have been tested for pregnant women in MAT; this intervention has the capacity to shift the clinical practice paradigm to give more emphasis on tobacco use. Finally, it is likely that B-EPIC will have significant impact on maternal and infant health outcomes, while also imparting a profound reduction on healthcare utilization.

### Study Procedures

One hundred pregnant women undergoing medically-assisted treatment (MAT) with buprenorphine for opioid dependence will be recruited and randomized to B-EPIC ( $n=50$ ) or TAU ( $n=50$ ). UK Departments of OBGYN/Maternal Fetal Medicine, College of Nursing, and UK Center on Drug and Alcohol Research will manage the program (letters of support provided from Co-Is in each of these departments).

**Table 2. Estimated retention at each perinatal period**

	2 nd Trimester (18-24 weeks)	3 rd Trimester (30-36 weeks)	Postpartum (1-2 months)	Postpartum (5-6 months)
Usual Care	50	45	39	28
B-EPIC	50	45	39	28
Total	100	90	78	56

**Inclusion criteria:** 1) current diagnosis of opioid dependence with participation in the buprenorphine treatment program; 2) less than 32 weeks gestation; 3) age 18-49 years old; 4) diagnosis of current tobacco use disorder; and 5) read or write in English. **Exclusion criteria:** Women are excluded if they have current prisoner status, current severe mental illness (e.g., bipolar disorder with current mania, current suicidal ideation), or alcohol or sedative/hypnotic dependence that requires medical intervention.

**Recruitment, Screening and Informed Consent:** Institutional Review Board (IRB) approval will be obtained from the University of Kentucky for this study. The screening, recruitment and retention plan is anchored by our previous work among pregnant and postpartum women who smoke. All study personnel will have completed human subjects training - and good clinical practice (GCP) research training. There will be two methods of recruitment: 1) study flyers will be posted in highly visible areas in the UKHC MAT clinics for pregnant/postpartum women and 2) the research nurse will provide an overview of the B-EPIC study in the buprenorphine treatment clinic for pregnant women. At conclusion of the overview, all women will be given a flyer in which they can either check that they are interested in screening for the study, verbally let the research nurse know they are interested in screening, and also be given the study recruitment phone number. Volunteers interested in the study will be screened for eligibility by research staff and those meeting initial eligibility screening criteria will be invited to come in for an in-person screening whereby informed consent will be completed before any study procedures are initiated (see Human Subjects).

**Randomization:** After informed consent and screening are completed, participants meeting study inclusion/exclusion criteria will be randomized (1:1) to the B-EPIC group (tobacco intervention) or TAU tobacco treatment (control group). All will continue to receive opioid dependence treatment with buprenorphine, regardless of treatment assignment. Randomization will be stratified by age (30+ vs less than 30). We will create a separate randomization schedule for each age stratum using the PLAN procedure in SAS (SAS Institute, Inc.); each schedule will include 17 blocks of 6 participants, with half per block randomized to each of the two treatment groups. Recruitment in this fashion will ensure an approximately equal number of subjects in each group throughout the enrollment period in both age strata, and we will continue recruitment until we have enrolled 100 subjects.

**Study Procedures.** Participants will be asked to provide urine samples and complete a survey at four times throughout the study (2nd and 3rd trimester, and 1-2 months, 5-6 months after delivery). There will be minimum of 8 weeks between individual data collection time periods. First, a survey available via iPad (paper/pen by request) will be administered by the research staff. The survey will take approximately 20 minutes to complete and will assess current and past use of tobacco products, demographic and psychosocial variables, stage of change, and personal characteristics; skip patterns will be used if indicated to minimize respondent burden. See Table 4. The survey will be stored on RedCap, a secure web-based data management system managed through the UK Clinical and Translational Research Center. The research nurse will then collect prenatal biomarkers (urine for cotinine and drug testing). [name] (PI) will train all study personnel collecting prenatal biomarkers consistent with procedures refined in previous studies. Participants will be informed their urine will be tested for cotinine (metabolite of nicotine) and other illicit drugs to confirm tobacco and/or illicit substance use at each data collection point and informed of their results in compliance with American Congress of Obstetricians and Gynecologists (ACOG) clinical standards. Participants will be informed their survey and biomarkers results will remain confidential. Confidentiality will be maintained through the use of non-identifying subject numbers; all study data will be saved daily on a secure server in a password-protected folder.

**Follow up data collection:** Healthcare outcome data will be collected from the mother's and infant's electronic medical record and national MEPS data. Maternal data obtained includes: prenatal history, medications and complications, gestational age at birth, birthweight, delivery method and complications, hospital readmissions, medical care adherence/attendance, readmission, emergency room visits and number of positive urine drug testing results. Infant data obtained from the maternal medical record or national MEPS data includes: sex and birth weight, NICU admission, length of NICU stay, NAS scores, treatment offered for NAS/total mg dose in morphine equivalents of such treatment, infant outpatient visits, including, well-child, sick visits and emergency department. Our team has successfully established methods to increase retention through the perinatal period by encouraging open and engaging communication. Various communication methods include: regularly scheduled (monthly) contact, telephone calls, post cards, emails, and text messaging. Preferred methods of communication will be used (as indicated by the participant).

**Compensation:** Participants are compensated for study completion in the form of gift cards (\$20-\$40 value). Gift cards are given in-person at prenatal and postpartum appointments. To bolster retention in the postpartum period we have increased the gift card value from \$20 to \$40. Participants will receive an additional \$20 gift card if three of four data collection points are completed. Refer to Table 3.

**Usual Care (TAU):** Women enrolled in the control group are informed of the risks of tobacco use and benefits of quitting using the ACOG 5'A's approach (see Box 1) by their healthcare provider. This standard takes approximately 5-15 minutes, and is offered at each prenatal and postpartum appointment.

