**Table 3. Summary of Study Design**

Timepoints	B-EPIC -Taking Action	Biomarkers	Survey	Incentives
Baseline 2nd trimester (18-24 weeks)	
 
• Individualized tobacco treatment (every month-minimum) plus supplemental counseling
 
• Biomarker validation and feedback
 
• Focus and adoption of health behavior and change in maternal thought process (e.g. exercise) based on PI framework
 
• Pharmacotherapy as needed.
 
	
 
• Urinary Cotinine
 
• iCup Drug & Quantitative Analysis
 
	
 
• Prenatal History
 
• Demographics
 
• Adverse Childhood Events (ACE)
 
• Outcomes Measures Survey (SOMs). Refer to Table 4
 
	\$20 gift card
3rd trimester (30-36 weeks)		
 
• Urinary Cotinine
 
• iCup Drug & Quantitative
 
	
 
• Prenatal History
 
• SOM
 
	\$20 gift card
Postpartum (1-2 months)		
 
• Urinary Cotinine
 
• iCup Drug & Quantitative
 
	
 
• Labor and Birth History
 
• Newborn History
 
• SOM
 
	\$40 gift card
Postpartum (5-6 months)		
 
• Urinary Cotinine
 
• iCup Drug & Quantitative
 
	
 
• Maternal and Infant Outcomes
 
• SOM
 
	\$40 gift card*

\*If 3 of 4 timepoints are completed, participants receive an additional \$20.

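### The under-32-week eligibility limit does not match the prenatal visit schedule: entry after 24 weeks rules out the stated baseline window, and entry after 28 weeks rules out both prenatal windows

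*Combined protocol and SAP*

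**What the plan says.** The inclusion criteria (Study Procedures, below Table 2) require "less than 32 weeks gestation" and set no lower limit. The Randomization paragraph assigns women who meet the criteria after consent and screening, stratified by maternal age only, until 100 are enrolled.

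Participants give urine and "complete a survey at four times throughout the study": second trimester, third trimester, and 1-2 and 5-6 months after delivery. Tables 2 and 3 put the first collection at 18-24 weeks and the second at 30-36 weeks. Table 3 labels the first as baseline, and Table 2 expects all 100 women at it and 90 at the second. The Study Procedures paragraph adds: "There will be minimum of 8 weeks between individual data collection time periods".

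The SAP (Data Analysis, Aims 1-2) puts group, time and their interaction in every mixed and GEE model. It does not say whether time means nominal visit or actual gestational age. Gestational age at enrolment is not among the listed covariates.

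**The concern.** Eligibility runs up to 8 weeks past the end of the baseline window (32 - 24 = 8). The plan does not say how to schedule, label or analyse visits for a woman who enters in that interval. This is a conflict between stated rules, not a missing detail.

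Three things are at stake:

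- **Comparability of the prenatal visits.** A late entrant's first collection carries a second-trimester label that may not fit. At 30 weeks or later it falls at the same gestational age as another woman's second visit.
- **Missing second visits.** For entry after 28 weeks the earliest permitted second visit comes after 36 weeks, so delivery may come first. Gestational age at birth is itself an Aim 2 outcome that B-EPIC is hypothesized to lengthen. The missing-data section relies on missingness at random and does not discuss this route of loss.
- **Uneven exposure.** Late entrants have much less time on B-EPIC before delivery. Gestational age at enrolment is also a lower bound on gestational age at birth: a woman enrolled at 31 weeks cannot deliver before 31 weeks. No model is required to adjust for it.

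**Working it through.** The plan states no figure on this point, so there is none to reproduce. The check is arithmetic on the stated windows.

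**Inputs**
- Eligibility below 32 weeks (inclusion criteria).
- Baseline at 18-24 weeks and second visit at 30-36 weeks (Tables 2 and 3).
- Minimum gap of 8 weeks (Study Procedures paragraph).
- Preterm cut-off of 37 weeks (Table 4), used only for the exposure range.

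**Formulas.** Let g be gestational age at enrolment.
- Earliest baseline: b = max(g, 18). It is in window if b ≤ 24. This assumes that a woman enrolled before 18 weeks waits for her baseline.
- Earliest second visit: v = max(30, b + 8). It is in window if v ≤ 36.

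| Entry (weeks) | Baseline in 18-24? | Earliest second visit | In 30-36? |
|---|---|---|---|
| up to 24 | yes | 30 to 32 | yes |
| over 24 to 28 | no | over 32 to 36 (26 + 8 = 34) | yes |
| over 28 to under 32 | no | over 36 to under 40 (31 + 8 = 39) | no |

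For entry at 30 to under 32 weeks, the baseline itself lies inside the second-visit window.

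**Postpartum visits.** These can meet the 8-week rule. With the second visit at 36 weeks and delivery at 37, the next collection is due no earlier than 36 + 8 - 37 = 7 weeks postpartum, which is within 1-2 months. From 2 to 5 months postpartum is 3 months, about 13 weeks.

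**Share affected.** The documents give no entry distribution, so this is an assumption: entry uniform from L to 32 weeks.
- Share after 24 weeks = (32 - 24)/(32 - L)
- Share after 28 weeks = (32 - 28)/(32 - L)

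| L (weeks) | After 24 weeks | After 28 weeks |
|---|---|---|
| 8 | 8/24 = 33% | 4/24 = 17% |
| 12 | 8/20 = 40% | 4/20 = 20% |
| 18 | 8/14 = 57% | 4/14 = 29% |

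For comparison, Table 2 allows for 100 - 90 = 10 women lost between the first and second visits.

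**Exposure before 37 weeks.** Entry at 18 weeks gives 37 - 18 = 19 weeks. Entry just under 32 gives about 37 - 32 = 5 weeks. At the monthly minimum in Table 3, that is roughly four sessions against one.

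**The case against.** The strongest reply is that the mismatch is confined to late entrants and does not favour either arm. Much of it stands.

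- **Compatibility.** A reader might infer that the four rules can never hold together. They do hold for anyone enrolled by 24 weeks, and between 24 and 28 weeks only the baseline window fails.
- **The 6-week gap.** The two windows taken alone allow 30 - 24 = 6 weeks between visits, which might look like a breach of the 8-week rule. It is not: a window and a minimum gap apply jointly, so a baseline at 24 weeks moves the second visit to 32-36 weeks.
- **How many women.** Nothing in the documents shows that many women are affected. The only hint, under Power Considerations, is that intake in the group's preliminary study was usually in the second trimester. That suggests fewer late entries than a uniform spread, though it describes another study and the criterion still admits them.
- **Bias.** Entry precedes 1:1 randomization, so late entry is balanced between groups in expectation. Any third-trimester visit can be lost to early delivery; late entry enlarges that loss but does not create it. The plan also has maximum likelihood, multiple imputation and last observation carried forward for missed assessments.
- **Covariates.** The SAP adds factors that differ between groups as covariates. That would bring in gestational age at enrolment only if it were tested and found to differ.

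None of this supplies a rule for women enrolled after 24 weeks, and no other section does.

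**Conclusion.** The point holds in a limited form. The eligibility limit conflicts with the baseline window for entry after 24 weeks, and with both prenatal windows, given the 8-week gap, for entry after 28 weeks. Those cut-points follow from the plan's own figures and need no assumption. The percentages do: they rest on uniform entry and may overstate the problem.

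The expected consequences are added noise in the prenatal comparisons, uneven prenatal exposure and extra missing second visits. A direct bias between groups is not shown.

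A reader might go further and conclude that the time factor is mislabelled in every model. The documents do not support that. Time as nominal visit number remains valid, the two postpartum visits are timed from delivery, and gestational age at birth, birthweight and NAS do not depend on the survey windows. The label misleads only for late entrants, and only if the prenatal visits are read as fixed gestational periods.

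The plan describes itself as exploratory and mainly aimed at estimating effect sizes. The point should be corrected, but it does not undermine the trial.

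**What to change.** 1. Reconcile the inclusion criteria, the 8-week rule in the Study Procedures paragraph, and the windows in Tables 2 and 3. State which rule gives way for a woman enrolled after 24 weeks and for one enrolled after 28 weeks. The choice is the sponsor's.
2. State in the SAP that time in the mixed and GEE models is nominal visit. Record the actual gestational or postpartum week at each collection. Actual week should not replace the visit label for out-of-window records only, because that would mix two time scales in one model.
3. Add a sensitivity analysis that excludes out-of-window prenatal visits. It may discard many baselines (33% to 57% under uniform entry), so it should stay secondary.
4. Pre-specify gestational age at enrolment as a covariate in the Aim 1-2 models, whether or not the groups differ on it.

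The cost is one clarifying amendment, a few lines in the SAP, one degree of freedom per model for a linear term, and a little more analysis. Eligibility screening already needs gestational age at entry. Recording it at each collection is not stated in the plan and would be a small addition.

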**Covariates.** Covariates will include demographic variables (age in years, education level, marital status, race/ethnicity), tobacco use and cessation history (e.g., average number of cigarettes smoked per day, severity of nicotine dependence, readiness to quit smoking), SHS exposure (smokers in the home), psychosocial measures (depression, anxiety, stress), use of other prescription medications (number), substance use severity (as measured by composite scores in the ASI-Lite), number of recent days of illicit substance use (using ASI for alcohol and other illicit drug use specifically illicit opioids, cocaine, marijuana/THC, benzodiazepines, and methamphetamine), and urine drug test results (positive/negative for marijuana, non-prescribed opioids, benzodiazepines, cocaine, methamphetamine). Covariates will be measured at baseline and at each data collection time-point (with the exception of demographic variables, which are not expected to change) Given the pilot nature of this study and the number of control variables, ability to detect differences in groups may not be possible; however, these data will provide critical information about what baseline demographic, psychosocial and substance use characteristics may be most associated with outcomes.

**Aim 3 Measures:** Using methods described by Drummond and Gold we will assess the reasonableness of the B-EPIC intervention's costs in relation to clinical outcomes achieved and examine the potential for program costs to be offset by reductions in health care utilization. Three types of economic measures will be collected during

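### Baseline survey and urine are tied to 18-24 weeks and not required before randomisation, so for women randomised earlier baseline falls after assignment

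*Combined protocol and SAP*

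**What the plan says.** Study Procedures (Randomization) fixes the point of allocation in one sentence: "After informed consent and screening are completed, participants meeting study inclusion/exclusion criteria will be randomized (1:1". What screening contains is not listed. The recruitment paragraph says only that consent comes before study procedures start. The gestational entry criterion is "less than 32 weeks gestation", with no lower bound.

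The assessments are described separately: "Participants will be asked to provide urine samples and complete a survey at four times throughout the study", the first of them in the second trimester. The same paragraph adds: "There will be minimum of 8 weeks between individual data collection time periods". Table 3 labels the first row "Baseline 2 nd trimester (18-24 weeks". The sentence "First, a survey available via iPad (paper/pen by request) will be administered by the research staff" puts the survey ahead of the urine collection. It does not put either ahead of allocation.

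B-EPIC first appears in that same baseline row of Table 3, as "Individualized tobacco treatment (every month-minimum) plus supplemental counseling". The B-EPIC Intervention paragraph attaches sessions to scheduled perinatal appointments and does not date the first one.

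On use of the data, Measures (Covariates) says "Covariates will be measured at baseline and at each data collection time-point", demographics excepted. The list includes cigarettes per day, nicotine dependence, readiness to quit, depression, anxiety and stress. The Statistical Analysis Plan (Aims 1-2) compares covariates between groups at baseline and carries factors that differ into the models for maternal-child outcomes. Its description of the mixed and GEE models then adds covariates for group differences in more general terms.

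**The concern.** Allocation is tied to consent and screening, while baseline is tied to gestational age. Nothing links the two. A baseline value is useful because assignment cannot have influenced it, and the plan does not secure that.

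Three uses are exposed. First, in the baseline comparison a difference caused by assignment would look like chance imbalance. Second, in the group-by-time models the first time-point may already contain some treatment effect, which weakens the interaction. Third, a difference arising after assignment may be adjusted for, which removes part of what is being estimated.

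Knowledge of the arm adds to this. B-EPIC brings a 60-minute first session with a tobacco treatment specialist on top of usual care of 5-15 minutes, and no blinding is described. Self-reported smoking and readiness may therefore differ by arm for that reason alone, even when a woman enters within 18-24 weeks but answers the survey after allocation.

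Power Considerations says the main purpose of the comparisons is to estimate effect sizes for larger studies, so any distortion would carry into their planning.

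**Working it through.** **Nearest stated figures.** The plan gives no number on the order of steps. The closest are the power figures for baseline comparisons in Power Considerations.
- t-test: 50 per group, difference 0.6 SD, alpha 0.05 (two-sided assumed). Noncentrality = 0.6 × √(50/2) = 0.6 × 5 = 3.0, with 98 degrees of freedom. Power is 84.4%, against the stated minimum of 84%.
- Chi-square: 60% versus 30%, 50 per group. Power is 81.5% with continuity correction (86.6% without), against the stated minimum of 81%.

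Both are reproduced and neither is disputed. They show that the baseline comparison is a planned, powered step.

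**Early entry.** Let g be the gestational week at randomisation. If randomisation takes place at entry, baseline follows it by 18 − g to 24 − g weeks:
- g = 8: 10 to 16 weeks
- g = 12: 6 to 12 weeks
- g = 16: 2 to 8 weeks

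The entry weeks are examples. The criteria allow all of them, but the documents do not say how many women enter then. The number of B-EPIC sessions falling in the gap cannot be derived, because the first session has no date.

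**Late entry.** For g above 24 and below 32 the baseline window has closed before the woman enters. With the 8-week spacing the next assessment is due no earlier than g + 8. Week 28 gives 36, the last week of the 30-36 window. Week 30 gives 38 and week 31 gives 39, both outside it.

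**Effect on the estimate (assumptions only).** Let e be the share of B-EPIC women whose baseline follows the start of treatment, and s the share of the effect already present at that baseline. A true change-from-baseline effect D is then seen as D × (1 − e × s).
- e = 0.1, s = 0.25: loss of 0.1 × 0.25 = 2.5%
- e = 0.5, s = 1: loss of 0.5 × 1 = 50%

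The documents give neither e nor s, and a range this wide means that the size is undetermined. The formula concerns change from baseline, and so the group-by-time interaction. It does not apply to the group main effect, to which an effect already present at 18-24 weeks still contributes.

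**The case against.** The best defence is that early entry may be uncommon. Table 2 shows 50 women per arm at 18-24 weeks, the same as the number randomised, and counts losses only from there. Handling Missing Data also starts attrition at the second trimester. Power Considerations describes intake in the team's preliminary study as typically in the second trimester. All of this fits enrolment at about the 18-24 week visit, and baseline could be taken at the in-person screening. These points make the problem likely to be smaller. They do not remove it, because no rule requires either arrangement.

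A reader might infer that women are randomised immediately on consent and have had several B-EPIC sessions before baseline. The documents do not support that. They give no interval between screening and allocation and no date for the first session, and Table 3 first lists B-EPIC in the baseline row itself. Nor do they support any particular percentage of dilution.

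The covariate route is also narrower than it may look. The explicit rule about factors that differ is written for maternal-child outcomes, and only the looser sentence on the models goes further. In its own repeated-measures model, the first value of cigarettes per day would normally be a response and not a covariate. The plan also admits covariates that are plainly post-randomisation, such as later time-point values and infant feeding at discharge. Fixing baseline does not settle those.

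**Conclusion.** The point holds in a limited form. As written, baseline comes after an evidently unblinded assignment for women randomised before week 18, and possibly after B-EPIC has begun. The plan does not use the term open-label; that is inferred from how visibly the arms differ. For women entering after week 24, a baseline in the stated window is impossible, and this needs no assumption about when sessions start.

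The first part follows from the entry criterion, the randomisation sentence and Table 3 taken together. The consequence is possible contamination of the baseline comparison, of the interaction and of some covariates. Its size depends on the share of early entrants and the timing of the first session, which the documents do not give. No stated sample size or power figure is shown to be wrong. The correction is worth making because it is cheap and the trial exists mainly to supply effect sizes.

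**What to change.** In the Randomization and Study Procedures paragraphs and in Table 3, require the survey and urine (cotinine and iCup) after consent and before the allocation is generated or revealed, at whatever gestation the woman enters. Define this assessment as baseline, and treat only its values as baseline covariates. Record gestational age at baseline so that it can be described.

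The work can be done at the in-person screening already planned, using a survey of about 20 minutes and urine tests already in the schedule. No sample size or power figure changes.

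There is a price. The first time-point is no longer confined to 18-24 weeks, so the labels in Tables 2 and 3 change. Early entrants wait longer for the 30-36 week assessment: a baseline at week 10 leaves 30 − 10 = 20 to 36 − 10 = 26 weeks. If a common 18-24 week measurement is still wanted for these women, it becomes a fifth assessment. For women entering after week 28, the 8-week spacing and the 30-36 week window still conflict, and those passages must be reconciled separately.
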